Participants will meet with study staff and will be verbally screened for eligibility based on the following criteria, by study staff at each clinic.

CAB participants: CABs operate in each CHC clinic and are comprised of community zone leaders in the clinic catchment area; as zone leaders, they educate their community on the study objectives and sensitize their community on study goals, risks and benefits. Eligible CAB members will be men and women aged >18, representing a ward within each experimental CHC site catchment area. Twenty Community Advisory Board (CAB) member participants will be recruited from CABs at each clinic (20 CAB members x 4 clinics, n = 80), and each attendee will be compensated ~\$US10 per visit.

Focus Group participants. Stakeholder participants will be recruited from ANCs to attend gender specific focus group discussions (FGDs). A total of 8 pregnant couples from each of the 4 experimental CHC clinics (8 couples per clinic) will be recruited for this study [2 gender specific FGDs per clinic; (8 men and 8 women) x 4 clinics = 64 participants]. Both members of each couple must enroll to participate. Eligible participants will be pregnant couples (men and pregnant female partners) aged >18, attending the antenatal clinic of the experimental CHC. No personal, individually identifying information will be collected and no individual interviews or assessments will be conducted with FGD Members. Each attendee will be compensated ~\$US10 per visit.

IRB Study Number:

Version #, Date:

S&S+LFLS Participants. Pregnant couple participants (300 couples, n = 600 participants) will be recruited over 18 months via referral from ANC/VCT and enrolled as couples. A total of 75 pregnant couples will be recruited from each of the 4 clinics participating in LFLS (75 pregnant couples per clinic x 4 clinics = 300 couples = 600 individual men and women.) Both members of each couple must enroll to participate. Eligible women will be pregnant (up to 6 months pregnant), aged >18, any HIV status, and the partner of a male participant enrolling (neonates undergoing EIMC are receiving a clinical service approved by parents; only parents are study participants). Eligible men will be aged > 18, any HIV status [in accordance with Zambian and WHO/UNAIDS (2016) policy for MC eligibility], and the partner of the pregnant female participant enrolling. There is no upper age limit for participation, and each person will be compensated ~\$US10 per visit.

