8) Number of Subjects*

A total 744 individuals will be recruited; 300 couples (600 men and women) and 144 CHC Community Advisory Boards members, patient focus group members, and EIMC experts.

9) Study-Wide Recruitment Methods*

Participants will be recruited by the community health center staff by referral to the study staff at the clinic site and by word of mouth only. Clinic sites are in Lusaka Province, and were reviewed and approved by the Lusaka Provincial Health Officer leadership. Following guidelines for site VMMC accreditation (Health Professions Council of Zambia, 2010), the following criteria governed selection of 8 clinic sites: 1) a community clinic catchment area of >30,000; 2) 2 health care providers available at site for VMMC/EIMC training and provision; 3) >2 voluntary counseling and testing (VCT) counselors and antenatal clinic (ANC) staff available for S&S+LFLS training, 4) space for VMMC/EIMC, 5) > 150 births per month, 6) a maternity ward. Clinic selection (n = 8) focused on spatial separation between clinics to avoid clinic contamination. CHCs will be visited by the research team to introduce the study to relevant staff, and staff members will refer clinic patients (couples intervention and focus groups) based on study criteria from those attending the ANC and VCT clinics. Senior staff will refer CAB members for participation. EIMC experts are consultants on the project.

Experimental sites only –participants are only recruited at experimental sites.

Clinic leaders and health care providers will be briefed on the study and study eligibility by the study team.

Potential patient candidates for couples and focus groups attending the clinic for HIV testing or pregnancy will be briefed on the study, and if interested, will be referred by clinic health care providers at the voluntary counseling and testing site and the antenatal clinic site (ANC) to the study staff.

Clinic leadership will provide referrals to CAB members to attend CAB meetings.

IRB Study Number:

Version #, Date:

Participants will meet with study staff and will be verbally screened for eligibility based on the following criteria, by study staff at each clinic.

No materials will be developed for recruitment flyers, etc. as this is not needed.

10) Study Timelines*

LFLS TIMELINE: Activity & Month	M1-3	M4-6	M7-9	M10-12	M13-15	M16-18	M19-21	M22-24	M25-27	M28-30	M31-33	M34-36

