Following baseline assessments, couples will complete a brief Stages of Change questionnaire prior to each prenatal and one-week post-partum LFLS sessions. Couples will be assessed at 6 months post-partum to evaluate EIMC and VMMC uptake by father, sons and infant to examine the interactive influence of EIMC and VMMC uptake, as well as the role of both parents, family members, peers and HIV serostatus in the decision-making process (Montaño et al., 2018; Mavhu et al. 2017; Cook et al., 2015; [name], Cook et al., 2014) (see Assessments).

13) Data and Specimen Banking* n/a

14) Data Management*

Analytic Plan and Power Analysis

Aim 1. Develop, pilot and conduct formative, process and outcome evaluations to assess the CHC level feasibility and acceptability of S&S+LFLS.

Aim 2. Assess the intrapersonal, interpersonal, structural, and sociocultural factors relevant to the LFLS intervention, and develop program components to respond to these factors.

Hypothesis 2. Father's circumcision status, paternal grandparents' circumcision attitudes, peer circumcision attitudes, father's HIV status, and mother's HIV status will be indirectly related to the decision to choose EIMC through the father's circumcision attitudes. A mother's circumcision attitudes will be influenced by her HIV status, and her protective attitudes toward the newborn which will also influence the father's circumcision attitudes.

Aim 3. Assess whether the combined S&S + LFLS pilot program will increase uptake of EIMC at clinic level.

Hypothesis 3. The S&S + LFLS experimental condition clinics will have significantly higher numbers of EIMC in comparison with observation condition clinics.

Hypothesis testing. The analyses for this feasibility pilot study will begin with examination of frequencies, means, skewness, and kurtosis across study variables (EIMC, VMMC, HIV status, attitudes) to assess normality. We will conduct 1) analysis of qualitative data, 2) a path model to explore undergirding sociocontextual factors of a father's decision to elect EIMC or VMMC for his male children, 3) a test of comparison between conditions.

IRB Study Number:

Version #, Date:

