H2. Assess factors relevant to the LFLS model. To investigate the indirect effects of the five main predictors (paternal grandparents' circumcision attitudes, peer attitudes surrounding circumcision, father's HIV status, father's circumcision status, and mother's HIV status) on infant circumcision, a path analysis (Kline, 2011) will be conducted. To estimate the indirect effects, it will be specified that the paths between the five main predictors on infant circumcision will act through father's circumcision attitudes. Mother's circumcision attitudes will be regressed on mother's HIV status, and a regression path between father's and mother's attitudes toward circumcision will be specified. When estimating the indirect effects, results will be adjusted for the effect of number of siblings circumcised.

All potential indirect effects will be estimated by a bootstrapping approach (MacKinnon et al., 2007). R-square of indirect effects will be used as measures of effect size (Fairchild et al., 2009). A sandwich estimator will be used to account for the nested data structure (e.g., individuals are nested by clinics). This estimator uses the Huber/White correction and adjusts for potential underestimated standard errors and bias in chi-square computation (Liang & Zeger 1986).

Missing data will be handled using Full Information Maximum Likelihood estimation procedures (Enders & Bandalos 2001). For model fit evaluations, we will use well-established fit indices and cutoff values: A well-fitting model ideally will have a non-significant model χ^2 , a Comparative Fit Index / Tucker-Lewis Index greater than .95, a root mean square error of approximation less than .08, and a standardized root mean square residual less than .08 (Hooper et al., 2008). All analyses will be conducted in Mplus (V8; Muthén & Muthén, 2017).

H3. Effect of S&S + LFLS pilot. To compare the proportion of EIMCs in the experimental group to the proportion found in the observation group, a one-sample z-test will be conducted. The population proportion will be taken to be the midpoint of the findings from Waters et al. (2013) on neonatal circumcision and historical numbers of circumcisions from Zambian clinics and hospitals. Based upon this rationale, the percentage of EIMCs in the observation group is anticipated to be approximately 5.0%.

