Exploratory analyses. To investigate change in EIMC attitudes, Stages of Change scores will be examined over time using an autoregressive modeling approach specifying the individual's stage at 1-week postpartum as the main outcome and individual's stage at baseline as a main predictor in the regression model (Hamaker et al., 2015). Variables from the previous path model will be included as potential covariates in attempting to explain stage movement. The estimated regression coefficient will reflect changes in EIMC attitudes over time. The model will use an ordinal logistic model to examine change over time. Odd ratios will be estimated as a measure of effect size (Chen et al., 2010).

Power. Using a two-tailed Z test to test the difference in proportions between two conditions at an α level of .05, this study has over 80% power to detect a difference of 6.0% in EIMC rate between the two conditions. This difference in proportion translates to an effect size of an odds ratio (OR) = 2.4, which is considered a small (OR = 1.68) to medium (OD = 3.47) effect size, according to Chen et al. (2010). This 2.4 OR is based on an effect size found in previous research examining circumcisions ([name] et al., 2015). With these specified parameters, 80% power is achieved with 140 couples (out of ~151 couples with male infants).

Data Security. CAB and FGD participants will not provide any uniquely identifying information during participation in group discussion sessions. Pregnant couple participants in the intervention will be assigned a unique code upon entering the study. This number will identify all participant files, which will include no identifiable information. Access to the computer data files will be restricted by password codes. The list translating participant number to identifying information

IRB Study Number:

Version #, Date:

will be maintained in a secure locked file in the Spear & Shield study office in Lusaka at the University of Zambia School of Medicine. Participants will be made explicitly aware at the time of the informed consent of the nature of the separate record that will be kept for them. CAB and focus group discussions will be audio-taped for review and summary of key discussion points; copies will be stored in a locked cabinet at the PI's Lusaka offices, and deleted following summarization.

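### The stated power covers about 140 infants of enrolled couples against a fixed 5% reference, whereas Aim 3 and Hypothesis 3 are stated for clinics, where the direct effect is diluted to about 0.17 points

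*Combined protocol and SAP*

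**What the plan says.** All references are to the combined protocol and SAP.

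- **Aim and hypothesis (section 14).** Aim 3 is to "Assess whether the combined S&S + LFLS pilot program will increase uptake of EIMC at clinic level". Hypothesis 3 expects significantly more EIMCs at experimental than at observation clinics.
- **Test (section 14, H3 paragraph).** For the comparison of EIMC proportions, "a one-sample z-test will be conducted" against a fixed population value. The plan expects that "the percentage of EIMCs in the observation group is anticipated to be approximately 5.0" (per cent). It does not say what the denominator of the proportion is.
- **Power (section 14).** The paragraph describes a "two-tailed Z test to test the difference in proportions between two conditions at an α level of .05" and states that "this study has over 80% power to detect a difference of 6.0% in EIMC rate between the two conditions", equated with an "effect size of an odds ratio (OR) = 2.4". It reaches 80% with 140 of about 151 couples who have male infants.
- **Who receives LFLS (section 7).** "75 pregnant couples per clinic x 4 clinics = 300 couples", enrolled over 18 months (section 10, months 7 to 24).
- **Clinic size (sections 9 and 24).** Each of the eight clinics must have "> 150 births per month".
- **Observation clinics (section 12, Design).** They recruit nobody and report clinic totals only.

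**The concern.** The power statement and the hypothesis refer to different populations. The sample size counts enrolled couples with a boy, but the hypothesis counts all EIMCs at a clinic. Enrolled couples are a small part of each clinic's births, so an effect of the planned size among them is heavily diluted in the clinic total.

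A reader who takes the power sentence as support for Hypothesis 3 would credit the clinic comparison with a sensitivity that the plan has not shown. If the background rate is near 5%, a flat clinic-level result would say little about whether LFLS works in the couples who attend. The study is a pilot meant to inform a later trial (section 12), so the unit to which each result applies should be clear.

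**Working it through.** **Inputs from the documents:** two-sided alpha 0.05; reference rate 5%; difference 6.0 points, hence 11%; n = 140 of about 151; more than 150 births per clinic per month; 4 experimental clinics; 18 months; 300 couples. **Assumptions:** half of births are male (in line with about 151 of 300); enrolled infants are counted at their own clinic; no effect on non-enrolled families.

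**1. Reproducing the stated power.** One-sample z-test:

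power = Φ[(|p1 − p0| − 1.96·√(p0(1−p0)/n)) / √(p1(1−p1)/n)]

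With p0 = 0.05, p1 = 0.11, n = 140: (0.06 − 1.96 × 0.01842) / 0.02644 = 0.904, and Φ(0.904) = 81.7%. This matches the plan. A two-sample test with 140 per arm would have 45.6% power and would need 320 per arm for 80%. The stated figure therefore belongs to the one-sample test on enrolled couples.

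**2. Share of births reached.** 150 × 4 × 18 = 10,800 births, about 5,400 male. 300/10,800 = 2.78% of births; 151/5,400 = 2.80% of male births. Because 150 is a minimum, these are upper limits. Over the clinic data window (month 6 to month 30, section 12, item 8) the share of births falls to 2.0–2.1%.

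**3. Clinic-level difference through enrolled couples alone.**

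| Uptake among enrolled boys | Background | Clinic-level difference |
|---|---|---|
| 11% (planned) | 5% | 0.0280 × 6 = 0.17 points |
| 100% | 5% | 0.0280 × 95 = 2.66 points |
| 100% | near 0 | 2.80 points |

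In counts, the planned effect adds 151 × 0.06 = about 9 EIMCs, whereas 6 points on 5,400 male births is 324.

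**4. Spillover needed for 6 points.** For the experimental clinics to reach 11% overall with all 151 enrolled boys circumcised, uptake among the other boys would have to be (0.11 − 0.028)/(1 − 0.028) = 8.4%, up from 5%. If enrolled uptake is the planned 11%, the others must reach 11% too.

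**5. Clinic-level power.** Poisson comparison of totals, z = (E1 − E0)/√(E1 + E0), with E0 = 5,400 × background and E1 = E0 + 151 × (0.11 − background). The lower rates are from section 6: 1,181/362,078 = 0.33% nationally, and about 0.02% in EIMC-trained Lusaka clinics.

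| Background | E0 v E1 | z | Power |
|---|---|---|---|
| 5% | 270 v 279.1 | 0.39 | 6.7% |
| 0.33% | 17.8 v 33.9 | 2.24 | 61% |
| 0.02% | 1.1 v 17.7 | 3.83 | 97% |

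All three ignore variation between clinics, and the lower two assume that enrolled uptake still reaches 11%. At 5% background, a t-test of 4 v 4 clinics (1,350 male births each) with an assumed between-clinic coefficient of variation of 0.1 to 0.5 has 5.8% to 5.1% power.

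**The case against.** The best defence is that the Power paragraph names its unit: 140 couples with male infants. The H3 paragraph specifies a one-sample test against a fixed value, and for that test the figure is right. This stands. The arithmetic is sound, and a reader who inferred that the power calculation is wrong would go too far. What remains is that the same paragraph speaks of two conditions, that Hypothesis 3 is about clinics, and that no power is given for clinics.

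A reader might also infer that a 6-point clinic difference is impossible. The documents do not support that. They describe routes beyond enrolled couples: clinic sensitization (section 6, Innovation), advisory board members who inform their communities (section 7), and relatives invited to LFLS Session 2 (section 12). The plan neither quantifies these routes nor uses them in the power statement, and step 4 shows that the spillover would have to be large. The dilution limit therefore applies to the direct effect only.

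Third, the 5% background is an anticipated midpoint, and the 2018 rates quoted in section 6 are far lower. Hypothesis 3 is worded in numbers of EIMCs, and a count of about 1 v 18 could be noticed. This stands too: low clinic-level power is a finding at the plan's 5%, not at every rate in the documents.

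Finally, this is a feasibility pilot, and how its authors would read a null result is conjecture. That limits the consequence but does not remove the mismatch.

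**Conclusion.** The concern holds as a mismatch of population. The claim of over 80% power for 6.0 points is valid for about 140 infants of enrolled couples against a fixed 5%, and does not carry over to the clinic-level Hypothesis 3.

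Through enrolled couples alone, the planned effect is about 0.17 points at clinic level, with a ceiling of about 2.7 points from a 5% background and 2.8 from near zero. These sizes rest on the 150-birth minimum, an 18-month window, half of births male, and no spillover. Busier clinics or a longer window make them smaller.

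It would be too strong to conclude that the clinic comparison could never show an effect. At 5% background its power is about 7% at best under these assumptions. At 0.33% or 0.02% it is about 61% or 97% before variation among four clinics per condition is allowed for, and only if enrolled uptake still reaches 11%.

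**What to change.** Amend section 14 as follows:

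1. In the Power paragraph, say that the 80% power and 6-point difference apply only to infants of enrolled couples compared with the fixed reference, and not to the clinic-level Hypothesis 3. In the H3 paragraph, give the denominator of the EIMC proportion.
2. State the clinic-level difference that the direct effect can produce: about 0.17 points at 11% v 5%, at most about 2.7 from a 5% background and 2.8 from near zero. Say how detectability depends on the background rate.
3. Label the comparison of clinic EIMC counts descriptive.

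Optionally, separate enrolled from non-enrolled EIMCs at the experimental clinics by subtracting the enrolled-couple outcomes (section 12, item 7) from the clinic totals (item 8). Both are already collected. The result is approximate, because of loss to follow-up and procedures done elsewhere, but it gives some view of spillover without a new form.

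The cost is a few sentences of SAP text. Design, recruitment and data collection stay as they are. The downside is that the stated power for Hypothesis 3 becomes less favourable.

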interpersonal and structural level factors associated with EIMC, and factors associated with each level. Stem items were derived from previous research (e.g., Albert et al., 2011; Amuri et al., 2016; Mavhu et al., 2012; Mavhu et al., 2016; Plank et al., 2010; Waters et al., 2012) and will be presented as open-ended questions; time will be provided to address additional topics as they arise. FGDs will be approximately 1.5 hours in duration. Prior to study onset, additional stems may be proposed using an iterative, collaborative process involving the University of Miami/University of Zambia (UZ) study team, which includes psychologists, social scientists, a pediatrician, surgeons, an infectious disease physician, and psychometrists. Final stems will be reviewed and refined by the entire team prior to initiation of FGDs and CABs. CAB meetings (1 per clinic, 3 meetings, n = 80 persons) and FGDs (2 per clinic, each gender concordant, 8 FGDs, n = 64) will be audio recorded and transcribed by trained study staff from the UZ into English; FGDs and CABs will be conducted in private areas in CHCs. Field notes will be made by staff during FGDs, CABs and study-related CHC staff meetings; meetings will be summarized from field notes. The project coordinator and study staff are social scientists and are experienced in conducting FGDs.

Community Advisory Board (CAB) Members. CAB Members will meet for three formal group discussions in a private meeting room within their experimental clinic. CAB members will be asked to 1) provide input on cultural factors that influence attitudes, perceptions, and beliefs about EIMC within their communities and among the ethnic groups predominant in the Lusaka Province, and 2) provide input on the LFLS intervention and assessment content and information on community issues and concerns that could influence LFLS program uptake. CAB Members associated with each CHC will thereby facilitate the adaptation of the intervention strategies to the local culture and clinic culture, enabling LFLS to work with the community rather than imposing the program on the community. No personal, individually identifying information will be collected and no individual interviews or assessments will be conducted with CAB Members.

Focus Group Discussion (FGD) Members. FGD members will meet in gender concordant groups in a private room within their experimental clinic site; members will provide input on cultural factors that influence attitudes, perceptions, and beliefs about EIMC among pregnant couples. They will provide guidance on cultural attitudes, ethnic preferences, beliefs and perceptions surrounding EIMC among pregnant couples in Lusaka. FGD members will inform the study on local issues or community concerns that could influence program uptake. No personal, individually identifying information will be collected and no individual interviews or assessments will be conducted with FGD members.

23) Sharing of Results with Subjects*

No relevant information will be collected to share with participants.

24) Setting

Describe the sites or locations where your research team will conduct the research.

Proposed clinic sites (N=8) are to be drawn from n = 14 potential clinics in Lusaka Province, and were reviewed and approved by the Lusaka Provincial Health Officer leadership. Following guidelines for site VMMC accreditation (Health Professions Council of Zambia, 2010), the following criteria govern selection of 8 clinic sites: 1) a community clinic catchment area of >30,000; 2) 2 health care providers available at site for VMMC/EIMC training and provision; 3) >2 VCT counselors and antenatal clinic (ANC) staff available for S&S+LFLS training, 4) space for VMMC/EIMC, 5) > 150 births per month, 6) a maternity ward. Clinic selection (n = 8) will focus on spatial separation between clinics to avoid clinic contamination. Randomization. Clinics will be matched by catchment area size and historical EIMC/VMMC rates and randomized by a non-study member; statistician will be blinded to clinic assignment. Following site selection and randomization, CHCs will be visited by the research team to introduce the study to relevant staff. Sites will be reviewed for adequate space. Approval from the Research Ethics Committee and the Institutional Review Board will be obtained prior to any study activities.

Lusaka Province Community Health Clinics (CHCs). All CHCs identified in Lusaka Province for potential participation offer Voluntary Counseling and Testing (VCT) (Republic of Zambia Ministry of Health, 2013). All sites include qualified staff to provide leadership and to implement the Project, willingness to conduct sessions, adequate space to meet patients, and willingness to work with the Project to expand the delivery of VCT/ANC services to offer VMMC/EIMC services. CHC clinic doctors confirmed available staff, time, space and facilities, and required staff expertise and willingness for full participation in enrolling and assessing participants. Clinic sites acknowledged qualified VCT staff at all sites (i.e., having the minimum qualifications and experience to receive training), and a catchment area of at least 30,000 individuals. Finally, each site will establish special recruitment and follow-up efforts if necessary. Out of the available CHCs, all clinic sites have easy access by paved roads frequently traveled by local minibuses and taxis and with signs advertising the VCT program.

Lusaka Province & MC Attitudes & Culture. Lusaka Province has a population of 3,186,000. The provincial capital is Lusaka city, which is also the capital of Zambia. Lusaka Province is a link to all provinces, and people with different cultural backgrounds from other provinces and countries move to Lusaka looking for employment and other business ventures. The rate of traditional MC in Lusaka is estimated to be approximately 10.2% (Makawa, 2012), with an estimated HIV prevalence of 20.8%. Barriers to MC in Lusaka include fear of pain associated with the procedure along with the healing process. Fears related to the healing process have been perpetuated by reports of men who

IRB Study Number:

Version #, Date:

indicate that the healing process did not go well for them. Others also report a fear that one could die from the procedure (Mwale & Jairos, 2009).

Zambia has many native languages which are spoken across Zambia in combination with English, which is the official language of the country. All languages are often used along with English in schools and government publications. In the 2010 census, 34% of Zambians reported speaking Bemba as their primary language, whereas 15% spoke Nyanja, 11% Tonga and 6% Lozi (Central Statistical Office, 2012). English is only natively spoken by 2% of the population but is commonly spoken as a secondary language by Zambians.

Bemba and Nyanja and English are spoken in Lusaka.

Lusaka District (Urban). Lusaka is the largest city in Zambia, and is considered one of the fastest-developing cities in the Southern part of Africa. English is the official language of the city, but Nyanja and Bemba are also commonly spoken. Some of the sociocultural barriers to implementing HIV-risk reduction programs in Lusaka have been reported to be poverty and refugee status. In addition, the organizational structure in health care settings and HIV-related stigma have been identified as barriers to seeking care. Cultural characteristics, such as traditional gender roles combined with religious beliefs, are also factors that may inhibit men from considering undergoing VMMC (Auvinen, Kylma, Valimaki, Bweupe, & Suominen, 2013). Younger men in Lusaka assert they would be willing to consider circumcision if the services were more accessible and if more information was provided regarding the procedure (Chanda, Likwa-Ndonyo, Nzala, & [name], 2012).

Kafue District. Kafue is in southern Lusaka Province located to the north of the Kafue River. According to the 2010 census, Kafue has a population of approximately 219,000 people. In some areas of Kafue, such as Nyimba and Namalyo, HIV prevalence is estimated to be 23.7% or higher (Lungu & Husken, 2010). Under a regional program, the WorldFish Center in Zambia conducted research in the Kafue Flats to investigate the accessibility of health care services, as well as to identify factors that may potentially explain the increased risk of HIV/AIDS among fishing communities (Lungu & Husken, 2010). Those working in the fishing industry are among the most vulnerable to HIV infection, and female fish traders often visit fishing communities in search of fish. Transactional sex (“fish-for-sex”) is a common occurrence in the Kafue Flats, increased by the high demand for fish. Both male and female traders are at a higher risk of contracting HIV and STIs (Lungu & Husken, 2010).

Potential CHC study sites: Lusaka Province (8 to be selected)

- Bauleni (Lusaka District, large)
- Mtendere (Lusaka District, large)
- Chilanga (Lusaka District, large)
- Chongwe (Chongwe District, large)

IRB Study Number:

Version #, Date:

- Karakantapa (Chongwe District, medium)
- Kriskatumba (Chilanga District, medium)
- Chainda (Chongwe District, small)
- Mwembeshi (Chilanga District, small)
- CHC study sites: Lusaka Province (alternates)
- Chalimbana (Chongwe District, small)
